For participants randomized to the waitlist control group, the baseline visit will conclude with instructions for the waitlist period. Participants randomized to the immediate start group will immediately begin the first dietary counselling session. There is no predetermined time between baseline data collection and commencement of the intervention; once all baseline electronic data are collected, participants may schedule the first in-person visit which will include the collection of the remaining baseline data and the first intervention session.

The Intervention

The intervention will consist of seven dietary counselling sessions delivered over 12 weeks (one session every two weeks). Three visits (the first, fourth, and seventh) will take place in person and the remaining will take place by secure video platform. If participants do not have access to a computer or the internet, they may complete all sessions in person. In the event that COVID-19 restrictions change during study delivery, the number of virtual sessions may be altered in order to comply with local restrictions. The sessions will be 45 to 60 minutes in length.

Intervention Development

The dietary recommendations are based on the Mediterranean diet(35) with minor modifications based on the results of a recent scoping review which identified and collated all of the existing research on diet

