Final Dietary Counselling Session	-discussion about achievements made during the program and affirmations -discussion of long-term goals and strategies to maintain
-----------------------------------	--

Dietary Supplement

During the 12-week study period, participants will be supplied with an omega-3 capsule supplement (AquaOmega High EPA) and instructed to take a dose of four capsules, once daily (containing a total of 3456 mg of omega-3 fatty acids: 2659mg of Eicosapentaenoic acid (EPA), 532mg of docosahexaenoic acid (DHA), and 800IU of Vitamin D), with a meal. Significantly more trials have been completed using omega-3 supplementation in the treatment of depressive disorders than anxiety disorders(42). Recent guidelines recommend a daily dose of 1-2g of EPA with a ratio of EPA:DHA of at least 2:1 for the treatment of depression(43). Due to the lack of specific recommendations on dose of omega-3 use for anxiety, our intervention will draw inference from these guidelines on depression to employ a dose that has been shown to be beneficial in other psychiatric disorders. We have selected a high dose, high EPA formula in order to maximize the likelihood of detecting a signal of effect in the present pilot trial.

Concomitant Therapies

All concomitant medication, psychotherapy or natural health products will be allowed during this trial. In order to minimize the risk of adverse events related to hypervitaminosis D, participants who are supplementing 1701 to 4000IU of vitamin D daily at the time of screening will be eligible to participate if they agree to decrease their vitamin D supplementation to 1700 so that their total daily intake of vitamin D, including the study product, is 2500IU. Participants will be encouraged to continue all other previous treatments at the same dose for the duration of the trial, if possible, but allowed to make changes if recommended by their mental health care provider. Participants will be queried at baseline

and at each follow up visit about their use of medication, psychotherapy or natural health products and any changes will be recorded, analyzed, and reported.

Safety and Criteria for Withdrawal

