Compliance with the supplement will be assessed at the final visit. Participants will be instructed to bring back all study product bottles containing any remaining capsules. The remaining capsules will be counted and recorded by a member of the study team. Compliance with the supplement will be reported as a percentage based on calculating the amount of pills consumed in comparison to the amount expected according to instructions.

Statistical Analysis

Since the pilot study is not powered to demonstrate efficacy, analysis of the pilot study results will be strictly descriptive. Baseline demographics and outcome measures will be summarized by group as means and confidence intervals, medians and interquartile ranges, or percentages and confidence intervals as appropriate. Process evaluation will be described both quantitatively (percent screened positive for inclusion, percent of eligible patients who consent to participate, percent with significant protocol violations, etc.) and qualitatively (e.g., reasons for failing inclusion criteria, reasons for refusing to participate, participant impressions of the intervention, etc.). All participants will be analyzed in the group to which they were randomized. Missing data will be carefully documented to inform the design of the larger trial. Participants who complete the treatment but do not report a satisfaction level will be treated as 'unsatisfied.' No interim analysis will be undertaken. The study will be considered feasible if 50 participants are recruited within two years, and participants in the intervention group take at least 60% of the study product and attend at least 60% of the diet counselling sessions. The study will be considered acceptable if at least 70% of participants report that they were satisfied with the intervention. The statistical analysis plan for the full-scale trial is included in Supplemental file 5.

Data management

The collection and storage of data will be done according to Good Clinical Practice Guidelines. All study staff involved in the collection or entry of data will be trained by the trial coordinator and will complete

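### The capsule count asks for neither empty bottles nor a dispensing record, so bottles left at home cannot be told from finished ones and the 60% product criterion can be overstated

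*Combined protocol and SAP*

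**What the plan says.** The compliance paragraph at the end of Outcomes Measured sets out the procedure. Timing: "Compliance with the supplement will be assessed at the final visit". Return: "Participants will be instructed to bring back all study product bottles containing any remaining capsules". Count: "The remaining capsules will be counted and recorded by a member of the study team". The result is a percentage obtained by "calculating the amount of pills consumed in comparison to the amount expected according to instructions". The schedule in Supplemental File 2 agrees, marking compliance only at close-out.

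Statistical Analysis then uses the figure. Apart from the recruitment target, the trial is feasible if "participants in the intervention group take at least 60% of the study product and attend at least 60% of the diet counselling sessions". Whether the 60% applies to the group mean or to each participant is not stated.

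The documents are silent on three things: the number of capsules dispensed, whether empty bottles should come back, and how a bottle that does not come back is scored. Statistical Analysis does set a conservative rule for a missing satisfaction rating (a completer who gives none counts as unsatisfied), but it has no counterpart for capsules.

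**The concern.** A pill count needs a known starting number and an account of every container. Here the starting number is not recorded in the plan, and the return request is worded around bottles that still hold capsules. A participant who finished everything can comply by bringing nothing. A participant who stopped early and forgot bottles, or preferred not to show them, also brings nothing or too little. The count alone does not separate the two.

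Feasibility and acceptability are the primary outcome of this pilot, and product intake is one of the feasibility criteria. Under Safety and Criteria for Withdrawal, poor compliers stay in the study, so the people whose intake is hardest to measure can reach the final visit. Under the usual pill-count formula their error runs towards declaring feasibility.

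**Working it through.** The plan gives no compliance figure to reproduce, so this is direct arithmetic.

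**Inputs from the documents.** Dose, from Dietary Supplement: "instructed to take a dose of four capsules, once daily". Duration: 12 weeks, or 84 days. Threshold: "participants in the intervention group take at least 60% of the study product".

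**Assumptions.** Intake = dispensed − returned. Dispensed = 336, with higher values examined in step 3. The documents state neither.

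1. *Expected intake and threshold.* 4 × 84 = 336 capsules. 0.60 × 336 = 201.6, so 202 capsules are needed.

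2. *One participant who stops at day 42.* True intake is 4 × 42 = 168, and 168/336 = 50.0%, below the threshold.
   - All 168 left over are returned: (336 − 168)/336 = 50.0%, which is correct.
   - 34 are left at home and 134 returned: (336 − 134)/336 = 202/336 = 60.1%, above the threshold.
   - Nothing is returned: 336/336 = 100%, the same as a full complier.

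3. *Dependence on the number dispensed.* With a surplus, a full complier should have leftovers, and a zero return computes to more than 100%.
   - 360 dispensed: a full complier has 24 left; a zero return gives 360/336 = 107.1%.
   - 480 dispensed: a full complier has 144 left; a zero return gives 480/336 = 142.9%.

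   A zero return is then distinguishable from full compliance, but only if the number dispensed is on record. A partial return can still mislead. Assume 360 capsules in three bottles of 120. Someone who stops at day 28 has taken 112 (112/336 = 33.3%). Returning only the opened bottle with 8 left gives (360 − 8)/336 = 104.8%.

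4. *Group mean, with assumed rates and the 60% read as a mean.*
   - Of 25 people, 15 take 75% and 10 take 30%. True mean: (15 × 75 + 10 × 30)/25 = 57.0%, a fail. If 4 of the 10 bring nothing and score 100%: (15 × 75 + 6 × 30 + 4 × 100)/25 = 68.2%, a pass.
   - Stoppers take 33.3% and the rest 90%. With 60% stoppers: 0.6 × 33.3 + 0.4 × 90 = 56.0%, a fail. If half the stoppers return nothing: 0.3 × 33.3 + 0.3 × 100 + 0.4 × 90 = 76.0%, a pass.
   - Same intakes with 40% stoppers: 0.4 × 33.3 + 0.6 × 90 = 67.3%, a pass whatever the return behaviour under this formula. The true mean falls below 60% only when stoppers exceed (90 − 60)/(90 − 33.3) = 53%.

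5. *The opposite scoring.* With 40% stoppers who return nothing and are scored zero: 0.4 × 0 + 0.6 × 90 = 54.0%, a fail against a true 67.3%. Scoring non-return as not taken therefore has its own error.

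**The case against.** The instruction covers all bottles with capsules remaining. A participant who stops early and follows it brings back every part-used and unopened bottle and is counted correctly, so the error needs someone not to do as asked. That is right. A reader might infer that participants are told to return only part-full bottles and that this wording itself produces the miscount; the text does not say 'only', and it could loosely mean all bottles with whatever is left. What remains is that a compliance measure should not depend on full cooperation from poor compliers, and that non-return cannot be verified when empties are not requested.

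A reader might also infer that an early stopper necessarily gets the same score as a full complier. That needs 336 dispensed and non-return scored as taken, and the documents state neither (step 3).

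Other checks exist. The final visit is planned in person, so someone who arrives empty-handed can be asked, though no such step is written. Adverse effects and changes in other treatments are asked about during follow-up, so it goes too far to say that stopping could never come to light, but neither is a capsule log. The end-of-intervention Omega Score is an objective marker of exposure, but the plan uses it as a diet-quality measure and does not tie it to the criterion. Dietary fish, an example goal in Supplemental File 3, can also raise it.

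Finally, the failing scenarios in step 4 use assumed rates, some placed close to the threshold, and the trial is a descriptive pilot. Both points stand and limit the weight of the concern.

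**Conclusion.** The concern holds as a gap in measurement. The plan cannot distinguish unreturned bottles from finished ones, and under dispensed minus returned the 60% product criterion can be biased upward. For one participant the error can be large: 50% true intake reads as just over 60% with 34 capsules unreturned, and as 100% with none returned, if 336 were dispensed.

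The documents do not support saying that the criterion is biased, or that the feasibility conclusion will be wrong. Direction and size depend on the number dispensed, the rule for unreturned bottles, the non-return rate and whether 60% is a mean or a per-participant threshold, and none of these is given. If non-return were scored as zero or missing, full compliers would be the ones penalised or dropped. This is a cheap improvement that should be made.

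**What to change.** - Record the number of capsules dispensed to each participant.
- Reword the instruction so that participants bring back every bottle dispensed, empty or not, at the final in-person visit. A count at the fourth visit is a low-cost addition, since the plan already states: "Three visits (the first, fourth, and seventh) will take place in person and the remaining will take place by secure video platform".
- Compute intake as dispensed minus returned only for bottles accounted for.
- Report the 60% criterion twice: with unaccounted bottles scored as not taken (conservative, in the spirit of the satisfaction rule) and as taken. Neither alone is unbiased, because a full complier may have thrown empties away. If both figures fall on the same side of 60%, the conclusion does not depend on the rule.
- Show the end-of-intervention Omega Score beside the count as supportive information only.

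Cost: one reworded instruction, a dispensing record, one optional extra count at a visit already held in person, and possibly a less favourable compliance figure. No additional tests are needed.

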Beck Anxiety Inventory	X	W								X
Omega Score	X	W								X
Mindful Eating Questionnaire	X	W								X
PROMIS-29	X	W								X
International Physical Activity Questionnaire	X	W								X
Food Security Assessment	X									
General Self-Efficacy Scale	X	W								X
Adverse Events			X	X	X	X	X	X	X	X
Height and Weight	X	W								X
Lipid panel, Hemoglobin A1C, fasting insulin, fasting glucose, vitamin C, beta-carotene, C-reactive protein	X	W								X
Compliance										X

X: All participants W: participants allocated to the waitlist arm

Supplemental File 3: Summary of Behaviour Change techniques used and coding according to Behaviour Change Techniques (BCT) Taxonomy Version 1

Grouping	Behaviour Change Technique	Intervention Component
Goals and Planning	1.1 Goal setting (behaviour)	Participants will set goals based on diet recommendations (ex. Eat fish twice per week)
	1.2 Problem solving	Discussion of barriers that may interfere and strategies to overcome the barriers
	1.4 Action Planning	Facilitator will guide participant in selecting meal ideas and recipes based on goal and set

		a plan to consume those meals on certain days of the week
	1.7 Review behaviour goal(s)	Follow up visit will involve a review of the previous week's goals and based on the outcome, future goals will be generated or modified
Feedback and Monitoring	2.3 Self-monitoring of behaviour	Participants will be given a form to record their intake of the recommended foods on a daily/weekly basis. This exercise will be optional.
Social Support	3.1 Social support (unspecified)	Participants will be encouraged to identify a person in their life that could assist them in achieving the goal
Shaping Knowledge	4.1 Instruction on how to perform a behaviour	Facilitator will explain cooking techniques or recipes that the participant is not familiar with. Provision of access to videos on food preparation skills
	4.2 Information about antecedents	Discussion of how emotions can lead to eating behaviours
	4.4 Behavioural Experiments	Ask participants to try soothing or distracting activities when experiencing non-hunger food cravings
Natural Consequences	5.6 Information about emotional consequences	Facilitator will present evidence suggesting a relationship between better quality diet and better mental health
Comparison of behaviour	6.1 Demonstration of the behaviour	Provision of access to videos demonstrating cooking skills and recipe preparation
Associations	7.1 Prompts/cues	Instructions to place recommended food items in visible locations in their kitchen
Repetition and substitution	8.4 Habit reversal	Instructions to prepare meals at home rather than purchasing take out
Comparison of outcomes	9.2 Pros and cons	Encourage participant to consider the pros and cons of current dietary habits if there is ambivalence to change
Reward and Threat	10.4 Social Reward	Congratulate participant on achieving goals
Regulation	11.2 Reduce negative emotions	Teach self-regulation and relaxation techniques for use during non-hunger cravings
	11.3 Conserving mental resources	Advise to prepare food in bulk, pre-portion meals or snacks, pre-plan meals or grocery lists

Antecedents	12.1 Restructuring the physical environment	Advise to keep food that is meant to be eaten less often in location that is inconvenient to access.
Self-belief	15.1 Verbal persuasion about capability	Tell participant that they can successfully modify their diet despite barriers such as mental health symptoms
	15.3 Focus on past success	Encourage participant to describe occasions where they have been able to eat healthy foods

Supplemental File 4: Outcome assessment

Demographic Questionnaire

Age: (enter age in years)

Sex assigned at birth:

- Female
- Male
- Other

Marital status:

- Single
- Married/common-law
- Divorced
- Widowed
- Prefer not to answer

Employment status

- Employed full-time
- Employed part-time
- Self-employed
- Student
- Unemployed
- Retired
- Prefer not to answer

Ethnic Background

- Black (African, Afro-Caribbean, African Canadian descent)
- East/Southeast Asian (Chinese, Korean, Japanese, Taiwanese, Filipino, Vietnamese, Cambodian, Thai, Indonesian descent)

- Indigenous (First Nations, Metis, Inuk/Inuit descent)
- Latino (Latin American, Hispanic descent)
- Middle Eastern (Arab, Persian, Afghan, Egyptian, Iranian, Lebanese, Turkish, Kurdish descent)
- South Asian (East Indian, Pakistani, Bangladeshi, Sri Lankan, Indo-Caribbean descent)
- White (European descent)
- Another race category
- Do not know
- Prefer not to answer

Education: Please indicate your highest level of education completed

- No certificate, diploma or degree
- Highschool diploma or equivalency
- Apprenticeship or trades certificate or diploma
- College or other non-university certificate or diploma
- University diploma or certificate below bachelor level
- University certificate, diploma or degree at bachelor level or above

Income: Please indicate the range that includes your total annual household income.

- \$10,000 or less
- \$10,001 to \$20,000
- \$20,001 to \$30,000
- \$30,001 to \$40,000
- \$40,001 to \$50,000
- \$50,001 to \$60,000
- \$60,001 to \$70,000
- \$70,001 to \$80,000
- \$80,001 to \$90,000
- \$90,001 to \$100,000
- Greater than \$100,000

Smoking status

- Have you smoked cigarettes in the past year? Yes (If yes, 2 questions below)
- No

On the days that you smoke, how soon after you wake up do you have your first cigarette?

- A. Within 5 minutes
- B. 6- 30 minutes
- C. 31-60 minutes
- D. After 60 minutes

How many cigarettes do you typically smoke per day?

- A. 10 or fewer
- B. 11-20
- C. 21-30
- D. 31 or more

Alcohol consumption

- Average number of alcoholic beverages per week: _____

Satisfaction Survey

Diet Satisfaction

	Strongly Disagree	Disagree	Neutral	Agree	Strongly Agree
I enjoyed the foods I ate during this program.					
The recommendations were easy to follow					
I felt hungry while following the program recommendations.					
I missed some of the foods that I used to eat while following these recommendations.					
I think I will be able to follow these eating recommendations long-term.					
Eating according to the recommendations is affordable, compared to my usual eating habits.					
I believe my overall health and well-being improved because of changing my eating habits.					
When dining out, it was easy to find foods on the menu that fit with the recommendations.					
The recipes provided to me were helpful.					
The educational materials provided to me were helpful.					
The amount of time I spent preparing foods was reasonable.					

Program Satisfaction

	Strongly Disagree	Disagree	Neutral	Agree	Strongly Agree

My interactions with the research staff were professional.					
I was comfortable and had time to discuss my thoughts, questions and concerns.					
I felt as if my treatment plan was individualized to my goals, personal beliefs, values and cultural background.					
I felt that it was easy to schedule appointments.					
E-mails and phone calls were responded to in a timely manner.					
I would recommend a family member or friend to participate in this study.					
I was satisfied with the Omega-3 supplement.					
I would recommend the Omega-3 supplement to a friend or family member.					
Overall, my experience during this study was positive.					

Open text questions:

1. What did you like most about participating in this study?
2. What did you not like, or like least, about participating in this study?
3. Which resources were most helpful? (examples: recipes, handouts, educational materials, videos etc.)
4. Which resources were least helpful?
5. Do you feel that your expectations were met during this study? Please explain.
6. Do you have any further comments related to the how the study was conducted? (ex. the processes, the questionnaires, etc.)
7. Were there any things that you liked about taking the Omega-3 supplement?
8. Were there any things that you did not like about taking the Omega-3 supplement?
9. How can we make this study better in the future?
10. Any other comments, concerns, or suggestions?

Supplemental File 5: Statistical analysis plan for the full-scale trial

For the full-scale trial, the primary outcome (Beck Anxiety Inventory) will be analyzed in a two-stage manner. All participants will be analyzed in the group to which they were randomized. First, the change

in anxiety will be compared between the active group and the waitlisted controls at the completion of the 12-week intervention for the active group. Between-group differences will be tested using an ANCOVA analysis that compares 12-week anxiety measures between groups while controlling for baseline anxiety measure. The change in anxiety score from just prior to the 12-week intervention to just afterwards will be summarized for all patients, waitlisted or not, who do receive the dietary intervention. This will permit a more precise estimate (smaller confidence interval) for the magnitude of the benefit while preserving the rigor of the randomized controlled trial. As a secondary analysis, the ANCOVA analysis will be repeated adjusting for age, income, education, food insecurity, smoking, body mass index, alcohol consumption and physical activity level.

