The primary objective of the proposed pilot clinical trial is to assess the feasibility and acceptability of delivering a diet counselling plus supplementation intervention to adult women with generalized anxiety disorder (GAD) as measured by recruitment, retention, and intervention uptake. The secondary objectives are to evaluate changes in anxiety symptom severity, quality of life, diet quality, mindful eating behaviours, self-efficacy, and biomarkers, over the intervention period as compared to the waitlist control period. This trial will lay critical groundwork for a larger, adequately powered clinical trial, designed to assess the effectiveness of dietary counselling in the management of GAD.

Trial Design and Setting

This pilot intervention study will recruit 50 adult women with moderate to severe GAD and provide a dietary counselling intervention in combination with an omega-3 supplement that also contains vitamin D. A randomized, waitlist-controlled design will be used (Figure 1). The waitlist-control design was selected to allow for random allocation to a non-treatment condition while still allowing all participants to complete the intervention. Waitlist-control designs have been suggested to improve rigor and preserve ethical considerations for studies where participant blinding is difficult(32). Twenty-five participants will be randomized to begin the intervention immediately and twenty-five participants will be randomized to observe a 12-week waitlist period before completing the intervention. This trial will take place at a single site. The study setting is the community clinic in the Canadian College of Naturopathic Medicine in Toronto, Canada. The study has been reviewed by the Research Ethics Board of the Canadian College of Naturopathic Medicine (CCNMREB040.[name]). Any amendments to this protocol will be communicated to the Research Ethics Board and Health Canada (the regulatory

authority for clinical trials in Canada) and modified on the trial registry. The design of this study involved participation from people with expertise in nutrition, psychiatry, research methods, laboratory testing, culinary education, behaviour changes, and lived experience with mental illness.

[figure not shown]

Figure 1: Diagram of participant flow through the trial

Participants Eligibility

Inclusion criteria:

1. A person aged 18-65 years who currently identifies as a woman.

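### The full-scale plan takes the size of benefit from an uncontrolled pooled pre-post change and credits it with the rigour of the randomised comparison

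*Combined protocol and SAP*

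**What the plan says.** The protocol's Statistical Analysis section keeps the pilot analysis descriptive and refers the reader onward: "The statistical analysis plan for the full-scale trial is included in Supplemental file 5". The point therefore concerns the planned full-scale trial, not the pilot's results.

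Supplemental File 5 opens with an as-randomised rule: "All participants will be analyzed in the group to which they were randomized". It then sets out two stages for the primary outcome, the BAI.

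- Stage 1 is the randomised comparison at the end of the active arm's 12 weeks: "Between-group differences will be tested using an ANCOVA analysis that compares 12-week anxiety measures between groups", adjusted for the baseline score.
- Stage 2 is the change from just before to just after the intervention, "summarized for all patients, waitlisted or not, who do receive the dietary intervention".

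The plan justifies stage 2 as giving a "more precise estimate (smaller confidence interval) for the magnitude of the benefit while preserving the rigor of the randomized controlled trial". Stage 2 has no control subtraction and no period term, and nothing says it is an uncontrolled summary.

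**The concern.** The waitlist arm exists so that change which would have happened anyway can be removed from the estimate of benefit. Stage 1 does this and stage 2 does not, yet the only estimate and interval the plan ties to the size of the benefit are those of stage 2. There are three difficulties.

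1. **Target.** A pooled pre-post change contains natural course, any regression to the mean left after the baseline re-measurement, and the effect of other treatment changes. The pilot's Concomitant Therapies section asks participants to keep other treatments steady, "but allowed to make changes if recommended by their mental health care provider". If the full-scale trial keeps that rule, such changes enter the pooled estimate.
2. **Population.** Pooling the arms and keeping only those who receive the intervention departs from the as-randomised rule in the same paragraph. Waitlisted participants lost before starting drop out of the estimate.
3. **Precision.** The interval is narrower largely because no control mean has to be estimated. That is a gain for a different quantity.

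At stake is the headline effect size of the full-scale trial. It could carry a narrow interval centred in the wrong place, with a statement that randomisation protects it. Treatment expectancy is not counted here, because an open waitlist comparison leaves it in the ANCOVA estimate too.

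**Working it through.** The plan gives no effect size, SD, correlation or sample size for this analysis, so there is no stated figure to reproduce.

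**Assumptions.** Results are in SD units, with equal SD at each time and correlation r between successive measurements (0.3 to 0.7). N participants are randomised 1:1 and all start the intervention. N = 50 matches the pilot; N = 100 and 200 are illustrative. The effect is τ, and untreated improvement is u1 in weeks 0–12 and u2 in weeks 12–24.

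**What each stage estimates**

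- Stage 1: (τ + u1) − u1 = τ.
- Stage 2: the immediate arm improves by τ + u1 over its treated period and the waitlist arm by τ + u2 over its own. The pooled mean is τ + (u1 + u2)/2.
- The bias is b = (u1 + u2)/2. It does not shrink as N grows. It is upward if untreated participants improve and downward if they worsen.

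**Precision**

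- SE of pooled change = √(2(1 − r)/N). At r = 0.5 this is 0.141, 0.100 and 0.071 for N = 50, 100 and 200.
- SE of ANCOVA difference = √(1 − r²) × √(4/N). At r = 0.5 this is 0.245, 0.173 and 0.122.
- Ratio = √(1/(2(1 + r))) = 0.62, 0.58 and 0.54 at r = 0.3, 0.5 and 0.7.

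The plan is right that the interval is narrower.

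**Coverage of τ by the pooled 95% interval** = Φ(1.96 − b/SE) − Φ(−1.96 − b/SE). For example, at N = 50 and r = 0.5 with u1 = u2 = 0.2, b/SE = 0.2/0.1414 = 1.414, and coverage = Φ(0.546) − Φ(−3.374) = 71%.

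At r = 0.5:

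| Untreated improvement | N = 50, both periods | N = 50, first period only | N = 200, both periods | N = 200, first period only |
|---|---|---|---|---|
| 0 SD | 95% | 95% | 95% | 95% |
| 0.1 SD | 89% | 94% | 71% | 89% |
| 0.2 SD | 71% | 89% | 19% | 71% |
| 0.3 SD | 44% | 81% | 1% | 44% |

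In the first-period-only columns b is half the stated improvement. With 0.3 SD in both periods at N = 50, coverage runs from 57% at r = 0.3 to 22% at r = 0.7.

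**Simulation check** (8,000 runs, three time points, true effect 0.4 SD, r = 0.5, t intervals), for 0, 0.1, 0.2 and 0.3 SD:

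- Both periods: 0.948, 0.894, 0.717, 0.449 at N = 50; 0.950, 0.705, 0.201, 0.011 at N = 200.
- First period only: 0.950, 0.936, 0.894, 0.825 at N = 50; 0.951, 0.895, 0.702, 0.441 at N = 200.
- ANCOVA: 0.947 to 0.955 throughout.

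The small differences from the table at N = 50 come mainly from using t rather than normal limits.

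**Further illustrations** (separate simulation, 4,000 runs, N = 50, r = 0.5)

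- No effect at all, with u1 = 0.3 and u2 = 0.1: the pooled change averages 0.20 SD, and its interval excludes zero in 27.5% of runs (1 − 0.725). ANCOVA averages 0.00.
- Effect 0.5 SD, untreated participants worsening by 0.2 SD per period: the pooled change averages 0.30 SD, an understatement.

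**When the pooled change is still the closer guess.** Its root mean squared error is the smaller one while b is below √(SE²ANCOVA − SE²pooled). At r = 0.5 that is √(0.06 − 0.02) = 0.20 SD at N = 50, √(0.03 − 0.01) = 0.14 SD at N = 100, and √(0.015 − 0.005) = 0.10 SD at N = 200. The margin narrows in the larger trial for which this plan is written.

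**The case against.** The strongest reply is that nothing is lost. ANCOVA yields an adjusted difference with an interval, the plan does not say it will be withheld, and calling stage 2 more precise presupposes a stage 1 estimate to compare it with. The rigour phrase might describe the two stages together. Stage 2 is only to be summarised, and the plan is for a later trial that has no sample size yet.

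Part of this stands. The significance test is unaffected, the ANCOVA estimate could still be reported, and no pilot result changes. But reading the rigour phrase as covering both stages rescues the test and not the magnitude, because the sentence attaches the smaller interval to the benefit itself. Someone following the plan would put the pooled figure forward as the better estimate.

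A second reply is that drift may be small. Under the pilot rules, BAI is measured at screening and again at baseline. Treatments changed during the wait must be stable for four weeks before the intervention. Waitlisted participants start from their end-of-wait score and need not meet the entry threshold of 22 again. These points make equal drift in both periods the less favoured scenario and are why the first-period-only columns are shown. They limit the bias but do not make it zero, and the scheduled assessments provide no concurrent untreated group for the waitlist arm's treated period.

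**Conclusion.** The concern holds. The pooled pre-post change estimates the effect plus the mean untreated change, so it does not have the protection of randomisation that the plan claims for it. Its 95% interval covers the benefit at the nominal rate only if mean untreated change over the two periods is zero.

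The algebra needs no figures from outside the plan. The practical size does: untreated change, correlation and N are all assumed, and the direction of bias is unknown. For untreated improvement of 0.1 to 0.3 SD at r = 0.5, coverage ranges from 94% to 44% at N = 50 and from 89% to 1% at N = 200, depending on whether the drift is confined to the first period. This should be corrected before the plan is carried into the full-scale trial. It does not invalidate the stage 1 test or anything in the pilot.

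**What to change.** In Supplemental File 5, replace the two stage 2 sentences, including the claim about precision and rigour, with:

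> The effect will be estimated as the baseline-adjusted difference in week-12 BAI between randomised groups, with its 95% CI. The pre-to-post change among all who start the intervention will be reported by arm and pooled as an uncontrolled description, and will not be used as an estimate of benefit.

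The cost is wording only, with no new data, visits or design change. The reported interval for benefit becomes about 1.7 times as wide at r = 0.5 (1/0.577); at N = 50 the half-width goes from 0.277 to 0.480 SD. Also given up is the smaller root mean squared error of the pooled change when mean untreated change is below the break-even values in the working, but whether it is that small cannot be known in advance.
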